**Evaluate how Exposure to FCA may Impact Quality**

Case Dyads vs. Control Dyads. No differences are expected between these groups at baseline, only Case Dyads are exposed to FCA, and thus a post-only design is an appropriate study design to evaluate this question or purpose. Case and Control Dyads will provide post-surveys and clinicians will be interviewed.

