***Observe quality and performance indicators among usual oncology care in similar patient-caregiver population to compare with cases.*** From non-treatment sites, identify, recruit, consent, and enroll persons with lung cancer (newly diagnosed or recent recurrence of disease) and their caregivers into the evaluation study. Recruitment will continue until 25 patients and 25 caregivers are enrolled (Control Dyads). Electronic health records for patients (appointment, clinical, and patient-reported data such as the M.D. Anderson Symptom Inventory that is standard of care) and study questionnaires will be used to evaluate quality and performance indicators however, questionnaires will be fielded at the post-period only. Non-treatment sites will not provide FCA as standard of care and function as control sites. These sites will include Geisinger Wyoming Valley in Wilkes-Barre, PA (“GWV”), and Geisinger Community Medical Center in Scranton, PA (“GCMC”). A case-matched controlled design will be used to evaluate differences in quality and performance indicators between groups at the post-period only.

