This study is characterized as an exploratory evaluation as the design limits the generalizability of findings and these findings will be biased in several ways. First, the treatment clinic and clinicians have been intimately involved in the development and implementation of the FCA. This factor likely influences clinician adoption of the FCA in care and could be limiting factor in other settings where FCA may be tested. Additionally, sites were conveniently chosen and site-level factors may bias study findings. The administration of the study sites is centralized to infer some consistency with operational procedures however this is a limiting factor in this exploratory evaluation. Quality and performance metrics are not routinely collected in these outpatient settings. In the absence of system-level data to describe variation in care, the study will depend on study questionnaires to evaluate quality and performance, which is a limiting factor as the perspective is contained to the study participants rather than the aggregate patient-population at each site. Secondly, a convenient sample of patients receiving care at the study clinics will be recruited into the study on a first-come, first serve basis and without random assignment to treatment or control groups. Additionally, Case Dyads must enroll in MyGeisinger patient portal to use FCA and although not required for the study, we will encourage Control Dyads to enroll in MyGeisinger patient portal to minimize bias related to health literacy using technology. Another potential bias is that some caregivers may reside out of state and this distance may impact the quality of their relationship with the patient; every effort will be made to match Case and Control Dyads with similar spatial situations but this may be prohibitive given the project timeline. These factors limit the assumption that any observations associated with FCA are related to the treatment use as variation in patient factors or the quality of care at clinics may account for observed associations. Potential participants (patients) are reasonably expected to receive an intense, brief oncology care with multiple appointments thus offering the opportunity to measure the impact of FCA use. Dyads will not be randomly assigned to treatment or control but offered standard of care per the clinic site. The study team will provide hands-on technical assistance to Case Dyads and associated clinicians to facilitate implementation and observe key learnings. Changes from baseline to post-study period will be evaluated within the Case Dyads, but given the severity of the condition and brief study period, the project team expects to observe greater differences in post-study period indicators between Case Dyads vs. Control Dyads.

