## 4.2 Study Population

Participants will be enrolled across three Geisinger locations, Geisinger Medication Center, Geisinger Wyoming Valley Medical Center and Geisinger Community Medical Center. GMC will serve as the intervention site and GWV and GCMC as the control site. Description of all three locations are listed below.

**Geisinger Medical Center (GMC) - Danville** is a fully integrated, community-based, health system with teaching programs (medical students, residents, fellows and other healthcare professionals). GMC is a quaternary/tertiary care hospital, that includes the Janet Weis Children's Hospital, a neonatal intensive care unit; a Level I Regional Trauma Center; and the GMC Outpatient Surgery—Woodbine Lane Campus.

**Geisinger Wyoming Valley Medical Center (GWV)** is an acute/tertiary hospital and regional referral center serving the healthcare needs of northeastern Pennsylvania. It is an open staff

hospital with 981 physicians having medical staff privileges. Located in Plains Township, near Wilkes-Barre, PA, it is approximately 60 miles northeast of Danville.

GWV, including its South Wilkes-Barre ambulatory campus and a series of regional clinics, form the System's northeastern hub. GWV offers an expanding range of services through multiple clinical departments: medicine, surgery, anesthesia, anatomic/clinical pathology, emergency medicine, family practice, obstetrics and gynecology, pediatrics, neurosciences, oncology, trauma services, orthopaedics, transplant services and diagnostic imaging services. GWV operates a full-time hospitalist program. The hospitalists work in conjunction with admitting and referring physicians to care for patients admitted to the medical center.

**Geisinger Community Medical Center (GCMC)**, a Level II Trauma Center is located in Scranton, PA. G-CMC offers a complete continuum of educational, diagnostic, therapeutic and rehabilitative services and programs. The Emergency Medicine Department is home to the Northeast Pennsylvania Trauma Center. G-CMC provides complete cardiac services, including open heart surgery. Other services at G-CMC include; Orthopedics, Surgical services and Women's Radiological services.

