For every Case patient enrolled at GMC, a data analyst will run the algorithm to consume aggregate electronic health record data to find and create a database of potential participants that meet inclusion (and do not meet exclusion) criteria at control sites. A weekly occurrence of the eligibility list will occur however, depending on the rate of recruitment the study team will determine whether this needs to occur more frequently. Study team members will apply a 1:1 case-matched control strategy to identify potential control patients that match case patients in terms of sex, age category, lung cancer histology, and lung cancer clinical and/or pathological staging information. This will be done after the Case patient-participant has a Case caregiver-participant consented to ensure that Case Dyads are enrolled and available for matching. If a Case patient-participant has enrolled but the Case caregiver-participant fails to enroll, the Case patient-participant will still be eligible for the study however the study team will recruit a replacement Case Dyad with the goal of enrolling 25 Case Dyads. Case patient-participants without caregiver-participants will be removed from analyses. Similarly, if a Control patient-participant consents but a Control caregiver-participant fails to enroll, the study team will identify a replacement Control Dyad with the goal of enrolling 25 Control Dyads. Research assistants will use the database to run weekly reports to identify potential control patients at GCMC or GWV to approach for recruitment. The research assistants will verbally review the list of potential participants as well as the weekly MDC list at GCMC and GWV with clinical staff to validate that patients on the list meeting inclusion criteria and can be approached for recruitment. The research assistant will be available to speak with patients before or after their scheduled medical appointments.

For the purpose of study awareness, informational flyers will also be available to patients in the exam rooms, waiting rooms, and through Oncology Care's MDC (**Attachment X: Recruitment Flyer - Controls**).

Demographic information will be collected on all eligible participants who are asked to participate. This information will be collected as part of the Pre-Treatment Survey for Case

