The caregiver identified by the patient may not be present for appointments (e.g., caregiver resides out of state). In such cases, enrollment in the study will need to be coordinated over the phone and by email. When this occurs and as possible, the study team will match Case Dyads to Control Dyads who have remote caregivers, but given the logistics of enrolling Case patients, then Case caregivers, matching and recruiting Control patients, and then recruiting Control caregivers in the brief study period, this may be difficult to operationalize and therefore be a source of bias as the Dyads' situations differ by distance. The study staff will ask the patient to speak with the identified caregiver about their interest in participation. Once the study team receives confirmation from the patient, the RA will ask the patient to provide the caregivers name and contact information. The study team will then reach out to the caregiver to explain the study in more detail and determine their interest in participation (**Attachment V: RA Scripts**). The RA will facilitate the applicable MyGeisinger and Proxy Access (**Attachment S: Remote Caregiver Letter**) and send an e-mail to the caregiver to consent and complete the baseline survey (**Attachment G: Initial Recruitment Email Caregiver – Case**). Follow-up will be made in one week if the caregiver has not consented or completed the baseline survey (**Attachment H: Reminder – Pre-Treatment Caregiver Communication – Case**). Three total follow-up attempts will be made to non-responders approximately one week apart; attempts will be made if no data or incomplete data are received with the goal of obtaining completed surveys. Once the study team receives the completed survey, the caregiver will receive a \$25 gift card. The gift card will be mailed to each individual (**Attachment T: Compensation Letter**).

Once consent is obtained, the baseline survey is complete and all applicable MyGeisinger and proxy access has been set up, the RA will call the caregiver to activate them in FCA intervention, offer and provide technical assistance, and confirm that the participating caregiver has at least a basic level of comfort with the FCA (**Attachment V: RA Scripts**)

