### 4.8.1 Statistical Analysis Plan

The study team will describe quality and performance indicators observed among study participants and evaluate associations between 1) difference in quality of care (satisfaction, quality of life, burden, coordinated care) associated with FCA exposure (Case Dyads vs. Control Dyads, Post-Treatment Surveys only); and 2) change in quality of care (satisfaction, quality of life, burden, coordinated care) associated with FCA use (Case Dyads Pre-Treatment Surveys vs. Post-Treatment Surveys).

Case Dyads and Control Dyads demographic and clinical information and survey responses will be fully described using frequencies and percentages for categorical variables and mean and standard deviation or median and interquartile range for continuous variables distribution dependent. To evaluate the difference in quality of care associated with FCA **exposure** (Case v. Control) will be evaluated using chi-square test, t-tests and non-parametric univariate tests distribution dependent. Mean patient and caregiver scores will be calculated for each dyad and compared between groups. Sensitivity analyses may stratify by level of FCA use (low-moderate-high) per dyad and opportunity time for FCA exposure. Case to Control patient analyses and Case to Control caregiver analyses will also be performed to detect role-level differences in perceptions of quality and performance associated with FCA exposure. To evaluate the association of the change in quality of care associated with FCA **use** difference in response between pre- and post- surveys paired t-test or ANCOVA depending on data type and distribution. Within Case Dyads, patient means will be compared with caregiver means to detect difference in quality and performance perceptions based on role.

All statistical analyses will be performed using SAS v9.4 (SAS Institute, Inc., Cary, NC, USA). All statistical tests are meant to be descriptive since this is purely an exploratory analysis.

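### The post-only Case–Control contrast rests on an expectation of baseline equality that Section 4.1 does not support, and Section 4.8.1 does not say whether the 1:1 matching or any adjustment is used

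*Combined protocol and SAP*

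**What the plan says.** Section 4.6 makes the post-period difference between Case and Control Dyads the primary endpoint. Under the heading on exposure in Section 4.1, the reason for measuring both groups only at the end is: "No differences are expected between these groups at baseline, only Case Dyads are exposed to FCA, and thus a post-only design"; the sentence goes on to call that design appropriate.

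Earlier in Section 4.1 the protocol describes a convenience sample without random assignment and conveniently chosen sites. It warns that "variation in patient factors or the quality of care at clinics may account for observed associations". Exposure and site coincide (Section 4.2): "GMC will serve as the intervention site and GWV and GCMC as the control site". Portal and proxy access are entry criteria for cases only (Section 4.2.2).

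For controls, Specific Aim 3 says that "questionnaires will be fielded at the post-period only", and Section 4.5 agrees.

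The protocol also contains mitigation:
- Section 4.3 applies 1:1 matching, to "match case patients in terms of sex, age category, lung cancer histology, and lung cancer clinical and/or pathological staging information".
- Section 4.5 adds that, where possible, "the study team will match Case Dyads to Control Dyads who have remote caregivers", and warns that this may be hard to carry out.
- Section 4.1 says controls will be encouraged to join the portal and that site administration is centralised.

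For the exposure contrast, Section 4.8.1 says it "will be evaluated using chi-square test, t-tests and non-parametric univariate tests distribution dependent". It names "paired t-test or ANCOVA depending on data type and distribution" only for the pre–post change within cases. The optional sensitivity analyses stratify by FCA use and exposure time. Sections 4.8.1 and 4.8.2 call all tests descriptive.

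**The concern.** Two parts of Section 4.1 pull in different directions. One lists reasons why the groups may not be comparable. The other uses expected comparability to justify leaving out a control baseline. The documents cite no data for the expectation, and on the four survey domains it can never be checked.

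If a baseline gap exists, whatever part of it lasts to week 8 is included in the difference labelled FCA exposure.

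There is a separate issue of precision. The design is called case-matched, yet the analysis text does not say that the matching enters the Case–Control tests. A reader cannot tell which analysis will be run, and an unpaired one would discard precision in a small study.

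**Working it through.** **The plan's own figure.** There is no power calculation to reproduce. The 25 dyads per group in Section 4.2.1 follow from its feasibility rates: 153 × 0.5 = 76.5 (77); 77 × 0.37 = 28.5 (28); 28 × 0.90 = 25.2 (25). Section 4.8.2 says 50 per group. I use 25 and show 50 where it matters.

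**Assumptions.** The documents give no baseline gap, SD, correlation or significance level. I assume gaps in SD units, a two-sided 0.05 level and normal scores.

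**1. Baseline gap, post-only unpaired t-test, no FCA effect.** Bias = gap × share that persists. With n per group, the noncentrality is bias × √(n/2) on 2n − 2 degrees of freedom. Groups are treated as uncorrelated here.

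| Baseline gap | Share persisting | Bias (SD) | p<0.05, n=25 | p<0.05, n=50 |
|---|---|---|---|---|
| 0.3 SD | all | 0.30 | 18% | 32% |
| 0.5 SD | all | 0.50 | 41% | 70% |
| 0.3 SD | half | 0.15 | 8% | – |
| 0.5 SD | half | 0.25 | 14% | – |

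**2. Ignoring the pairs, 25 pairs.** The unpaired test takes the standard error to be √(2/25) = 0.283 SD. With within-pair correlation ρ, the true value is √(2(1 − ρ)/25). The paired noncentrality at 0.5 SD is 0.5 × √25 / √(2(1 − ρ)), on 24 degrees of freedom. The unpaired results come from simulation.

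| ρ | True SE | Type I error, unpaired | Power at 0.5 SD, unpaired | Power at 0.5 SD, paired |
|---|---|---|---|---|
| 0.1 | 0.268 | 3.9% | 41% | 43% |
| 0.3 | 0.237 | 2.1% | 40% | 53% |
| 0.5 | 0.200 | 0.7% | 38% | 67% |

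The unpaired test is conservative, and the point estimate is the same either way. Pairing does not remove a baseline gap: a persistent 0.5 SD gap with no FCA effect would be flagged by the paired test in the same 43% to 67% of studies.

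**3. What a control baseline survey would add.** The 95% half-width for the baseline gap is t(0.975, 48) × √(2/25) = 2.011 × 0.283 = 0.57 SD (0.40 SD at 50 per group). The bias left by ANCOVA is the post gap − r × baseline gap, where r is the baseline–post correlation. For a change score it is the post gap − the baseline gap. With a 0.5 SD baseline gap and r = 0.5:

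| Scenario | Post-only bias | ANCOVA bias | Change-score bias |
|---|---|---|---|
| Gap persists | 0.50 | 0.25 | 0 |
| Gap halves | 0.25 | 0 | −0.25 |
| Gap vanishes | 0 | −0.25 | −0.50 |
| No baseline gap; 0.5 SD site effect arises in follow-up | 0.50 | 0.50 | 0.50 |

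No method is unbiased in every row.

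**4. Lost partners.** Section 4.2.1 expects 90% completion. If losses are independent, 25 × 0.9 × 0.9 is about 20 complete pairs. An analysis limited to complete pairs would drop dyads that still carry information.

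**The case against.** The strongest reply is that the protocol has already said most of this. Section 4.1 states that findings will be biased, names site and patient factors, and leaves rigorous between-group testing to later studies. All tests are descriptive, so no confirmatory decision is at risk. Matching, portal encouragement and centralised administration give some support for comparability. All of this stands, and it lowers the severity. It does not support the specific expectation for the survey outcomes, which none of these measures covers.

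A second reply is that t-tests can be paired and that Specific Aim 3 calls the design case-matched. This also stands. A reader might infer that the contrast is definitely unpaired because pairing is named only for the within-case change. The text does not establish that; it is silent.

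A third is that the percentages are hypothetical and that the gain from pairing is small when ρ is low. Both are true. At ρ = 0.1 power rises only from 41% to 43%.

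A fourth is that a control baseline survey is a trade-off. The last table bears this out, so it should not be presented as a necessary correction.

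**Conclusion.** The point holds, at minor to moderate severity. The premise for the post-only contrast lacks support in the protocol and cannot be checked on satisfaction, quality of life, burden or coordination. The use of the matching, and of any adjustment, is unspecified.

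On assumed inputs at 25 per group, a persistent gap of 0.3 to 0.5 SD would give p<0.05 in 18% to 41% of studies with no FCA effect. Ignoring pairs would cost between 2 and 29 percentage points of power at 0.5 SD for ρ from 0.1 to 0.5 (43% − 41% and 67% − 38%).

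Two stronger readings are not supported. A reader might infer that the groups do differ at baseline; the documents give reasons for doubt but no evidence of a gap. A reader might also infer that ignoring the matching produces false positives; on its own it does the reverse. What is at stake is a descriptive estimate labelled as FCA exposure that mixes FCA with site and selection.

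**What to change.** 1. **Section 4.8.1.** Specify a Case–Control analysis that respects the matched pairs and keeps dyads whose matched partner is lost: a random pair effect for continuous scores, including dyad means, and a mixed logistic model for categorical outcomes. A conditional logistic analysis is an alternative, but it uses complete pairs only. Prespecify a small adjustment: days since the start of Oncology Care and treatment modality for all outcomes, plus caregiver age and gender for caregiver and dyad-mean outcomes. Leave out portal status, since cases must have or set up an account. Cost: SAP text, slight extra analysis work and a few degrees of freedom. Timing and modality should be derivable from the encounter dates and departments already listed.

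2. **Section 4.1.** Replace the sentence on baseline equality with a statement that groups are not randomised and may differ at baseline. List what the matching covers, including caregiver distance where possible. Report the result as a descriptive FCA-plus-site contrast. Compare early symptom-inventory values from the EHR as a partial check. It is partial because they are collected during active chemotherapy (Section 4.8.1, Data Sources), while patients on radiation alone are also eligible. Cost: wording and one descriptive table.

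3. **Optional.** Give Control Dyads the existing pre-treatment surveys at consent. Cost: an IRB amendment, 25 dyads × 2 people × $25 = $1,250 in gift cards, and added survey burden. It would estimate the baseline gap to about ±0.57 SD and would not remove site effects that arise in follow-up.

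The 25 dyads per group in Section 4.2.1 and the 50 in Section 4.8.2 must also be reconciled.

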#### Evaluate how Use of FCA may Impact Quality

The **second propose this project** is to evaluate how *use* of the FCA may impact quality indicators associated with oncology care. In this exploratory evaluation study, we aim to evaluate whether quality indicators change with exposure to FCA, thus pre-post difference within the Case group is an appropriate study design to answer this question or purpose. Future studies may use these exploratory evaluation findings to more rigorously evaluate or test

between group differences using appropriate study designs. Case Dyads will provide baseline and post-surveys.

NOTE: Throughout the protocol and IRB application we will refer to the study as the *Exploratory Evaluation of Family Caregiver Application*. In the consent form and other patient facing materials, we will abbreviate the project title and description to the *Care Coordination in Oncology Study*.

Also, the data analyst described throughout the proposal will serve in two roles 1) as a data analyst for research activities such as patient eligibility lists, recruitment reports, reporting needs, etc. and 2) as a data broker to maintain the application. The data analyst will be listed as research support staff in the IRB application given the research role.

## 4.2 Study Population

Participants will be enrolled across three Geisinger locations, Geisinger Medication Center, Geisinger Wyoming Valley Medical Center and Geisinger Community Medical Center. GMC will serve as the intervention site and GWV and GCMC as the control site. Description of all three locations are listed below.

**Geisinger Medical Center (GMC) - Danville** is a fully integrated, community-based, health system with teaching programs (medical students, residents, fellows and other healthcare professionals). GMC is a quaternary/tertiary care hospital, that includes the Janet Weis Children's Hospital, a neonatal intensive care unit; a Level I Regional Trauma Center; and the GMC Outpatient Surgery—Woodbine Lane Campus.

**Geisinger Wyoming Valley Medical Center (GWV)** is an acute/tertiary hospital and regional referral center serving the healthcare needs of northeastern Pennsylvania. It is an open staff

hospital with 981 physicians having medical staff privileges. Located in Plains Township, near Wilkes-Barre, PA, it is approximately 60 miles northeast of Danville.

GWV, including its South Wilkes-Barre ambulatory campus and a series of regional clinics, form the System's northeastern hub. GWV offers an expanding range of services through multiple clinical departments: medicine, surgery, anesthesia, anatomic/clinical pathology, emergency medicine, family practice, obstetrics and gynecology, pediatrics, neurosciences, oncology, trauma services, orthopaedics, transplant services and diagnostic imaging services. GWV operates a full-time hospitalist program. The hospitalists work in conjunction with admitting and referring physicians to care for patients admitted to the medical center.

**Geisinger Community Medical Center (GCMC)**, a Level II Trauma Center is located in Scranton, PA. G-CMC offers a complete continuum of educational, diagnostic, therapeutic and rehabilitative services and programs. The Emergency Medicine Department is home to the Northeast Pennsylvania Trauma Center. G-CMC provides complete cardiac services, including open heart surgery. Other services at G-CMC include; Orthopedics, Surgical services and Women's Radiological services.

